### 4.5 Association between patient's general optimism and their expected live birth rates

Furthermore, we will assess in the entire sample with linear mixed models including 'couple number' as a random factor to take account of clustering within couples, if patient's general level of optimism is associated to their expected live birth rate.

### 4.6 Association between IVF-live birth rates expected by patients and infertility specific distress

Whether the intervention and control group, differ in infertility specific distress on the day of their embryo transfer will be analysed by comparing both group's IDS-score with an independent sample t-test. A p-value  $\leq 0.05$  will be considered statistically significant and the mean difference in infertility specific distress between both groups and its 95%

confidence interval will be reported. In addition, a linear (mixed or non-mixed) model will explore in the entire sample whether IVF-live birth rates expected by patients are associated with their infertility specific distress. We will examine whether gender significantly ( $p \leq 0.05$ ) affects the association between the IVF-live birth rate expected by patients and their infertility specific distress. If it does, we will rely on linear (non-mixed) models per gender. If it does not, we will rely on linear mixed models while including 'couple number' as a random factor to take account of clustering within couples, as partners cannot be considered independent cases.

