## 0. Study synopsis

Study title	Gynecologists' feedback on ART-Pregnancy rates: a Randomized Controlled Trial
Short title	GAP-RCT
Sponsor name	KU Leuven
Principal Investigator	[name]. [name] (UZ Leuven)
Medical condition/ disease under investigation	Infertility treated with IVF
Study purpose	
We will examine the hypothesis that women who are given their personalized IVF-prognosis are less likely to overestimate their IVF-live birth rate, as compared to women who do not receive a personalized IVF-prognosis.
 
Control group: At the time of their fresh embryo transfer couples will receive a document with a photo of their transferred embryo(s) and the number of cryopreserved embryos.
 
Intervention group: At the time of their fresh embryo transfer couples will receive a document with the following feedback: a photo of their transferred embryo, the number of cryopreserved embryos, the quality rating of the transferred embryo's (i.e. ★, ★★, ★★★, ★★★★), and couple's personalized IVF-prognosis (i.e. their chance on a live birth from the current IVF-cycle, including the transfer of fresh and if available cryopreserved embryos, calculated by entering eight background characteristics and five IVF-laboratory results into a prognostic model).

Primary outcome	The proportion of women expecting their IVF-live birth rate to be double their calculated IVF-prognosis , directly after their fresh embryo transfer.
Secondary outcomes	
The proportion of men expecting their IVF-live birth rate to be double their calculated IVF-prognosis, directly after their fresh embryo transfer.
 
Women's and men's anxiety will be assessed with the reliable 'State-Anxiety Inventory, (STAI-state)' questionnaire, disseminated in coded paper-pencil format on the day of the fresh embryo transfer.
 
Patient's infertility-specific distress will be assessed with the reliable 'Infertility Distress Scale (IDS)' questionnaire, disseminated via text message and online within two days of the conclusive pregnancy test after the transfer of the last (fresh or cryopreserved) embryo of the studied IVF-cycle.

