## 1. Background and rationale

The general population is known to overestimate *in vitro* fertilisation (IVF) success rates. Qualitative interviews showed that well informed women cryopreserving their oocytes were unrealistically optimistic about their own chances of having a child as they thought they and/or their gynaecologist were better than average. To the best of our knowledge, the live birth rates expected by infertile couples during their IVF-cycle (i.e. in real life treatment situations) has yet to be studied. In addition, whether these expected live birth rates are affected by factors like gender, previous treatment experiences and level of optimism is unknown.

IVF-success rates expected by patients are especially relevant since patients shared in interviews that the combination of unrealistically high expected live birth rates and repeated unsuccessful IVF-cycles, caused distress, which ultimately led to discontinuation from IVF. The association between patient's expected IVF-success rates and their level of distress experienced at the time of a negative pregnancy test and decision to discontinue IVF has yet to be quantified prospectively.

Fertility patients have indicated that they want personalized information, for example on which success rate to expect. Recently, prognostic models that calculate personalized and cycle-specific success rates, have been developed and validated. So far, no study has examined whether gynaecologist's feedback to couples about their personalized IVF-prognosis influences patient's expected IVF-success rate.

Based on retrospective analysis of data from couples treated with a 2nd - 6th IVF-cycle by our laboratory, our group developed a model to give couples a personalized IVF-prognosis on the day of their embryo transfer based on eight background characteristics and five IVF-laboratory results from their current IVF-cycle. Our prognostic model performs exceptionally well as compared to previously published models. More specifically, our model has a c-statistic of 0.74 and the c-statistic of previously published IVF-models ranges between 0.50 and 0.73

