### 2.3 Study parameters/endpoints

The **primary endpoint** is the proportion of women expecting directly after their fresh embryo transfer that their IVF-live delivery birth rate to be double their calculated IVF-prognosis (i.e. women's expected live birth rate  $\geq 2^* \text{prognose}$ ) In addition the proportion of men expecting their IVF-live birth rate to be double their calculated IVF-prognosis will be studied. Patient's expected IVF-live birth rates will be assessed immediately after the fresh embryo transfer with a single question coded paper-pencil questionnaire.

**Women's and men's anxiety** will be assessed with the reliable 'State-Anxiety Inventory, (STAI-state)' questionnaire disseminated in coded paper-pencil format on the day of the fresh embryo transfer (Appendix 3). The STAI-state questionnaire includes 20 questions rated on a-four-point-Likert scale and results in a score between 20 to 80 (the higher, the more anxiety).

**Patient's infertility-specific distress** will be assessed with the reliable 'Infertility Distress Scale (IDS)' questionnaire, which has been translated reciprocally to Dutch (Appendix 4). The IDS questionnaire will be disseminated via text message and online within two days of the conclusive pregnancy test after the transfers of the last (fresh or cryopreserved) embryo of the studied IVF-cycle. The IDS questionnaire includes eight questions to be rated on a-five-point-Likert scale and results in a score between 8 and 40 (the higher, the more infertility specific distress, Appendix 4).

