### 3.2 Study procedures including recruitment and data-collection

The main outcomes of this study are gathered on the days of OPU and Embryo transfer as presented in figure 1.

[figure not shown]

Figure 1: Study procedure and data collection for participating couples of the GAP-RCT

**On the day of their oocyte aspiration**, couples will be informed on the study and asked for their informed consent. Consenting men and women of eligible couples will be asked to each fill out a questionnaire on expected live birth rate (Appendix 1) and the LOT-R questionnaire (Appendix 2) on general optimism.

**On the day of their fresh embryo transfer**, couples are randomized. Couples in the control group receive a document with a photo of their embryo(s) and the number of cryopreserved embryos. Couples in the intervention group receive a document with a photo of their transferred embryo(s), its quality rating, the number of cryopreserved embryos and couple's personalized IVF-prognosis (Appendix 5). Men and women of both groups will be asked to fill out the questionnaire on expected live birthrate (Appendix 1) and the STAI-state questionnaire on anxiety (Appendix 3).

**Within two days of the conclusive pregnancy test** after the transfers of the last (fresh or cryopreserved) embryo of the studied IVF-cycle, the IDS questionnaire on Patient's infertility-specific distress will be disseminated via text message and online (appendix 4).

**Eighteen months after the embryo transfer** of the last (fresh or cryopreserved) embryo of the studied IVF-cycle, the researchers will follow-up the long-term clinical and compliance outcomes in patient's medical chart (i.e. censored by their medical doctor to discontinue IVF, IVF-delay and IVF-discontinuation).

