### 4.4 Anxiety experienced by patients

Whether the intervention and control group, differ in anxiety on the day of their embryo transfer will be analysed by comparing both groups STAI-state with an independent sample t-test. A p-value  $\leq 0.05$  will be considered statistically significant and the mean difference in anxiety between both groups and its 95% confidence interval will be reported.

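### The expectation-distress model in section 4.6 does not separate positive from negative pregnancy tests, although the stated aim is distress at a negative test

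*Combined protocol and SAP*

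**What the plan says.** **The aim.** The background (section 1) reports interviews in which "the combination of unrealistically high expected live birth rates and repeated unsuccessful IVF-cycles, caused distress". It adds that the link between expected success and patients' "level of distress experienced at the time of a negative pregnancy test and decision to discontinue IVF has yet to be quantified prospectively". The third aim in section 2.2 carries this forward: it concerns distress when the test is negative.

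**Data collection.** The synopsis says the IDS is "disseminated via text message and online within two days of the conclusive pregnancy test after the transfer of the last (fresh or cryopreserved) embryo". Section 2.3 agrees: "The IDS questionnaire will be disseminated via text message and online within two days of the conclusive pregnancy test". Section 3.2 gives the same trigger: "after the transfers of the last (fresh or cryopreserved) embryo of the studied IVF-cycle, the IDS questionnaire on Patient's infertility-specific distress". None of the three makes sending the IDS depend on the result of the test.

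**The analysis.** Section 4.6 has two parts. The first is a randomised comparison by t-test of whether the arms "differ in infertility specific distress on the day of their embryo transfer will be analysed by comparing both group's IDS-score". The second is a linear model, mixed or fitted per gender, that "will explore in the entire sample whether IVF-live birth rates expected by patients are associated with their infertility specific distress". Neither part mentions the test result.

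**The concern.** The aim names one population (patients who have just had a negative test) and the model names another (everyone). A positive test plausibly changes both the level of distress and its relation to what the patient had expected. A slope fitted across both results can therefore differ from the slope the aim asks about, and could be reported as its answer. Leaving the population open also allows a choice between a pooled and a negative-only result after the data have been seen.

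The time point is a smaller matter. The sentence that defines the IDS comparison refers to a day on which the IDS is not given.

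**Working it through.** **1. Population, side by side.**
- Aim (sections 1 and 2.2): distress at a negative test.
- Collection (synopsis, 2.3, 3.2): after the conclusive test that follows the last transfer, whatever the result.
- Instrument (Appendix 4, item 1): asks about distress over a menstruation that meant no pregnancy. This fits a negative test, but a questionnaire item does not define an analysis population.
- Model (4.6): no restriction, stratification, covariate or interaction for the result.

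The aim and the model do not match. This needs no arithmetic.

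**2. When the slopes differ.** The documents give no SD, effect size or sample size for the IDS, so there is no figure of the plan's to reproduce. The algebra for a regression on expected rate alone shows what matters. Let
- p = share of respondents with a positive test;
- b and b₊ = slopes after a negative and a positive test;
- Δ = mean expected rate, positive minus negative;
- δ = IDS difference, positive minus negative, at the same expected rate;
- V = variance of expected rate.

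(a) Same slope in both groups (b₊ = b): pooled slope = b + p(1−p)·Δ·δ / V.

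If expectation tracks prognosis (Δ > 0) and distress is lower after a positive test (δ < 0), the pooled slope is pulled downward. If Δ or δ is zero, there is no shift.

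(b) Slopes differ, with Δ = 0 and equal spread of expectation: pooled slope = (1−p)·b + p·b₊.

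This equals b only if b₊ = b. Section 1 attributes distress to high expectations combined with failed cycles, so a different slope after a positive test is plausible. Adding the test result as a main effect removes shift (a) but not shift (b).

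**3. Illustration of (a); every input is assumed.** A simulation took about 33% pregnant, expectation correlated with prognosis, an IDS SD of 6 and a true negative-test slope of zero.

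| Fall in IDS with pregnancy (points) | Pooled slope, IDS points per 10 points of expected rate | Negative-test slope |
|---|---|---|
| 0 | about 0.0 | about 0 |
| 4 | about −0.20 | about 0 |
| 8 | about −0.41 | about 0 |

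The shift is proportional to δ, as the formula requires: 0.20/4 and 0.41/8 are both about 0.05. The largest value is 0.41/6 ≈ 0.07 SD per 10 points. In the couple-level mixed model both partners share the test result, so shift (a) enters only through differences between couples. It would be diluted there, not removed.

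**4. Precision cost of restricting the model.** The standard error is proportional to 1/√n. For an assumed 20% positive, 1/√0.8 = 1.12; for 40%, 1/√0.6 = 1.29. This takes residual variance and spread of expectation as unchanged. The 64 women per group in section 3.1.2 are not the base for this model: they are sized for the primary endpoint, and the model also includes men.

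**5. Time point.** On transfer day section 3.2 lists only the expected-rate question and the STAI-state; the synopsis adds two feasibility questions. Section 4.4 uses the same phrase for anxiety, asking whether the arms "differ in anxiety on the day of their embryo transfer will be analysed by comparing both groups STAI-state", and there it is correct. Carry-over from 4.4 is the likely cause.

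**The case against.** The strongest reply is that the entire sample means both arms together, as it appears to in 4.5 and 4.7. Section 4.6 would then be silent on the test result rather than deciding to mix results. That reading is fair, and a reader should not infer a deliberate choice to pool. The gap remains, because nothing elsewhere limits the IDS or the model to negative tests.

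It can also be said that the model is exploratory and unpowered, and that the amount of mixing is unknown. Both stand. The IDS follows the last fresh or frozen transfer. Read literally, couples who conceive with embryos still frozen may not reach that trigger, so the positive share among respondents could be lower than in the cohort.

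Four stronger readings are tempting but not supported:
- **A transfer-day IDS is missing, or the comparison cannot be done.** Three places fix the time point, and no data set or test changes.
- **The randomised IDS comparison should also be limited to negative tests.** The negative-test aim is not stated for it, and the restriction would condition on an event after randomisation.
- **The exclusion of PGD couples loses its basis.** Section 3.1.1 rests it on the expectation-distress association in general, not on the negative-test version.
- **The bias has a known size or direction.** Both depend on relations the documents do not report.

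**Conclusion.** The concern holds for the exploratory association model. As written, it can include patients with either result and does not estimate the association named in the third aim. The pooled slope departs from the negative-test slope if expectation tracks prognosis and distress is lower after a positive test, or if the slope differs by result. If neither condition holds, there is no shift. The documents do not allow the departure to be sized; the simulated values only show that it can occur.

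The transfer-day phrase is a wording error with no effect on results. Severity is minor to moderate: a secondary, exploratory analysis is affected, while the primary endpoint and its sample size are not.

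**What to change.** In section 4.6:

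1. Fit the association model in patients whose conclusive test after the last transfer was negative. As a sensitivity analysis, fit all IDS respondents with test result and its interaction with expected live birth rate, and report the negative-test slope.
2. State that the randomised IDS comparison uses all IDS respondents and is not restricted by test result.
3. Replace the transfer-day time point with the one given in section 2.3.

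This changes analysis-plan wording only. No questionnaire or visit is added: the test that triggers the IDS supplies the result, and the chart follow-up in section 2.4 already relies on failed tests. The price is fewer patients in the exploratory model, with the 12-29% larger standard error worked out above, or less if few respondents have a positive test.

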Background variables	The following variables that potentially affect patient's expected live birth rate will be extracted from patient's medical file: whether they already had an ART-child (i.e. yes/no) and how many unsuccessful embryo transfers they had in the past (i.e. number). In addition, both partner's general optimism, will be assessed with the reliable questionnaire 'LOT-R' which will be disseminated in coded paper-pencil format on the day of oocyte aspiration.
Feasibility outcome	On the day of their fresh embryo transfer, men and women will be asked to fill out two questions on uptake and evaluation of the standardized personalized feedback.

Follow-up outcomes	Long-term clinical and compliance outcomes will be followed-up in couple's medical chart 12-18 months after the oocyte aspiration. More specifically, the 12-months cumulative clinical live birth rates for the observed oocyte aspiration will be extracted from the medical chart. In addition, the following compliance outcomes will be extracted: (i) censored by their medical doctor to discontinue IVF (yes-no) , (ii) number of untreated cycles within 12-months after oocyte aspiration and prior to the start of a new fresh cycle while not pregnant (i.e. IVF-delay), (iii) whether or not a subsequent IVF-cycle was started within twelve months after the last failed pregnancy test while not pregnant and no medical censoring to discontinue (i.e. IVF-discontinuation).
Study design	RCT (computerized randomization; 1/1 allocation sequence; no blinding)
Endpoints	The expected IVF live birth rate, anxiety and infertility specific distress of women and men.
Sample size	Hypothesizing that the intervention can lower the proportion of women expecting their live birth rate to be double their calculated IVF-prognosis from 50% to 25% dictates a sample size of 64 women per group (two-sided test; power 80%; $\alpha=0.05$ ; G*Power). To account for a 15% chance of study drop-out due to not filling-out the questionnaires or loss of follow-up, 74-80 women will be recruited per group .

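### The exploratory expectation–distress model in section 4.6 leaves out general optimism, which is measured in both partners before feedback, so its slope is open to confounding of unknown size and direction

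*Combined protocol and SAP*

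**What the plan says.** Section 4.6 contains two analyses of the IDS distress score. The first compares the randomised groups with a t-test. The second, which is the subject here, is a linear model that "will explore in the entire sample whether IVF-live birth rates expected by patients are associated with their infertility specific distress". Gender is examined as a modifier of that association. If it modifies it, separate models are fitted per gender; if not, "we will rely on linear mixed models while including 'couple number' as a random factor to take account of clustering within couples". No covariates are listed.

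Optimism appears elsewhere in the plan:

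- The synopsis (Background variables) says "both partner's general optimism, will be assessed with the reliable questionnaire 'LOT-R", and section 3.2 has consenting partners complete "the LOT-R questionnaire (Appendix 2) on general optimism" on the day of oocyte aspiration. The feedback document follows at embryo transfer.
- The same synopsis entry opens with "The following variables that potentially affect patient's expected live birth rate will be extracted from patient's medical file" and then adds optimism to that group of variables.
- Section 1 says that "whether these expected live birth rates are affected by factors like gender, previous treatment experiences and level of optimism is unknown".
- Section 4.5 will assess "if patient's general level of optimism is associated to their expected live birth rate", and states no direction.

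Section 4.1 also explores how partners compare and influence each other on optimism. Nothing in section 4 puts optimism into the distress model.

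**The concern.** The trial randomises feedback, not expectation. Pooling both arms to relate expectation to distress therefore uses mostly natural differences between people, and some of those may reflect disposition. If general optimism is related both to the expectation a person states and to the distress that person later reports, the crude slope mixes the two relations. A couple random factor does not adjust for an individual's own optimism, and neither does a gender check.

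Section 1 motivates this analysis with interview accounts in which high expectations, combined with repeated failure, led to distress. Readers will compare the slope with that account. A slope near zero, or a clearly positive one, could each be partly a product of optimism, and the planned output would not let a reader tell. The plan already holds the variable that would show it.

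**Working it through.** **The plan's own figures.** There is no sample-size calculation for the section 4.6 model. The only one (section 3.1.2) is for the primary endpoint: 50% versus 25%, two-sided 0.05, 80% power, 64 women per group. It reproduces with a two-sided Fisher exact test (power 0.794 at 63 per group, 0.802 at 64). It has no bearing on this point except to supply 2 × 64 = 128 women as a working sample size.

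**Formula.** With all variables standardised, let

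- b = slope of distress on expectation, given optimism;
- g = slope of distress on optimism, given expectation;
- r = correlation of optimism with expectation.

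The slope from a model without optimism is b + g × r, so the bias is g × r. The documents give no value for b, g or r, so every value below is an assumption.

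**Main range.** For r from 0.2 to 0.4 and g from −0.2 to −0.4:

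- smallest bias: 0.2 × (−0.2) = −0.04;
- middle: 0.3 × (−0.3) = −0.09;
- largest: 0.4 × (−0.4) = −0.16.

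A b of +0.15 would then appear as 0.15 − 0.04 = +0.11 at one end and 0.15 − 0.16 = −0.01 at the other.

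**Wider range, including zero and the opposite sign, with b = 0.20.**

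| r | g | bias g × r | slope without optimism | change |
|---|---|---|---|---|
| any | 0 | 0 | 0.20 | 0% |
| 0.1 | −0.2 | −0.02 | 0.18 | −10% |
| 0.2 | −0.3 | −0.06 | 0.14 | −30% |
| 0.3 | −0.4 | −0.12 | 0.08 | −60% |
| 0.4 | −0.5 | −0.20 | 0.00 | −100% |
| 0.3 | +0.3 | +0.09 | 0.29 | +45% |

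With a smaller b of 0.10, r = 0.3 and g = −0.4 give 0.10 − 0.12 = −0.02, a change of sign.

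**Against sampling error.** For 128 women the standard error of a small standardised slope is about 1/√126 = 0.089. The three biases in the main range are then 0.04/0.089 = 0.4, 0.09/0.089 = 1.0 and 0.16/0.089 = 1.8 standard errors. Using both partners would reduce the standard error somewhat, to perhaps 0.07, and 0.16/0.07 = 2.3. A bias of about two standard errors therefore arises only when both assumed values are at their extreme.

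**Effect on power (Fisher z, 128 women).** Power is 0.62 at a slope of 0.20, 0.35 at 0.14 and 0.14 at 0.08.

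**Does the covariate remove this bias?** In a simulation of 200,000 individuals with b = 0.20, g = −0.40 and r = 0.30, the slope was 0.082 without optimism (formula: 0.08) and 0.203 with it.

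**Cost in precision.** At r = 0.4 the covariate inflates the slope's variance by 1/(1 − 0.16) = 1.19, so the standard error rises by about 9%, before any gain from explaining distress.

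**The case against.** A reader might infer that the trial itself expects optimism to drive expectations, and that the slope is therefore likely to be biased against the positive relation described in the Background. The documents do not support this. Section 1 calls the optimism–expectation link unknown, section 4.5 asks only whether one exists, and the synopsis speaks of potential effects. No section links optimism to distress. Nor is the sign obvious for this instrument: the IDS in Appendix 4 includes items on the importance of having a child, on infertility as a challenge and on the strength of the wish for a child, and optimism need not lower these. This part of the objection stands in full.

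The second argument is that the analysis is exploratory and is worded as an association in sections 2.2 and 4.6. The trial's formal hypothesis (section 2.1) concerns overestimation, not distress, and a crude association is a legitimate descriptive quantity. This limits the importance of the point. It does not remove the value of showing whether the slope depends on optimism.

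The third is that LOT-R alone would not isolate an effect of expectation, because section 4.6 names neither the calculated prognosis nor the pregnancy-test result as a covariate. That is correct, and it is why the adjusted slope must be described with restraint. It is not a reason to leave out a baseline variable already in hand. LOT-R is completed before feedback, so it cannot be a consequence of the feedback, and the risk of over-adjustment is small.

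**Conclusion.** The point holds as a free improvement. The section 4.6 slope is open to confounding by a variable that the trial measures and itself tests as a correlate of expectations. The documents fix neither size nor sign. There is no bias if either link is absent. If optimists expect more and report less distress, the bias runs against the relation suggested in the Background: −0.04 to −0.16 SD per SD on the assumed range, or roughly half to about two standard errors. If optimists expect more and report more distress, it runs towards that relation. All of these sizes rest on assumed correlations, and the standard errors also assume about 128 women with usable data.

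The randomised comparison of IDS scores in the same section, the primary endpoint and its sample size are not affected. It would be too strong to say that the planned slope is wrong, or that a null result would be caused by optimism.

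**What to change.** In section 4.6, pre-specify the individual's own LOT-R total score as a covariate in the association model, in whichever branch is used (mixed model or separate models per gender). Report the expectation slope and its 95% confidence interval with and without it, on the same set of participants, so that a difference between the two is not due to missing LOT-R forms. Add one sentence saying that the adjusted slope remains an association and not an isolated causal effect. If the two slopes agree, the question about optimism is largely settled for the reader; if they differ, the reader needs to see both.

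The cost is a few lines in the analysis plan and one degree of freedom in an exploratory model. No new data, visits or participants are needed.

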## 3. Methodology

### 3.1 Study population and sample size

#### 3.1.1 Study population

##### Inclusion criteria:

All couples treated at the Sint Augustinus Fertility clinic (Wilrijk) with a 2nd-6th fresh cycle of IVF are eligible. IVF includes IVF with or without ICSI and every couple can only participate ones in this study. Couples treated with their first IVF-cycle are not eligible, since they are not the priority target population for this study. According to qualitative research discontinuation from IVF can amongst others be explained by the combination of high expectations regarding IVF-live birth rates and having experienced several cycles of unsuccessful IVF.

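### The exploratory model of distress on expected live birth rate (section 4.6) omits the count of past failed transfers that the trial already collects, so its slope is unadjusted and cannot show the expectation-with-failure combination in the rationale

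*Combined protocol and SAP*

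**What the plan says.** Section 4.6 has two parts. The first compares the Infertility Distress Scale (IDS) score between the randomised groups with a t-test. The second is the subject here: a linear model that "will explore in the entire sample whether IVF-live birth rates expected by patients are associated with their infertility specific distress". Besides the expected rate, section 4.6 names two elements. It checks whether gender "affects the association between the IVF-live birth rate expected by patients and their infertility specific distress". If gender does not, it uses "linear mixed models while including 'couple number' as a random factor"; if it does, it fits separate models for women and men.

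The synopsis (background variables) lists items to be extracted because they may affect the expected live birth rate, among them "how many unsuccessful embryo transfers they had in the past (i.e. number". Section 1 likewise names gender, earlier treatment and optimism as possible influences on expectation. Section 4 gives gender and optimism an analysis. It uses the count of past failures nowhere.

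On rationale, section 1 reports from patient interviews that "the combination of unrealistically high expected live birth rates and repeated unsuccessful IVF-cycles, caused distress", which in the end led to discontinuation. Section 3.1.1 explains the exclusion of first cycles by a similar statement about discontinuation: "the combination of high expectations regarding IVF-live birth rates and having experienced several cycles of unsuccessful IVF". Section 1 also says what has not yet been quantified prospectively: "The association between patient's expected IVF-success rates and their level of distress experienced at the time of a negative pregnancy test", together with the decision to discontinue. The third aim in section 2.2 is to explore that association.

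**The concern.** The slope is estimated over both groups together, across whatever expectations patients happen to hold, so randomisation does not protect it. A variable related to both expectation and distress will shift it. Past failure is the obvious candidate: the plan suspects that it affects expectation, and its rationale links it to distress, though only jointly with high expectation.

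The rationale also describes two things acting together. A model with one slope for all failure histories averages over them and cannot show whether the slope differs between couples with few and many failures.

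What is at stake is the interpretation of an exploratory result. A weak or null slope could be taken to mean that expectation matters little for distress, when it might reflect confounding or averaging over opposite patterns.

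**Working it through.** **Plan's own figure.** The documents give no figure for the section 4.6 model. The only calculated size is 64 women per group for the primary outcome. It reproduces: the two-sided Fisher exact test for 50% against 25% has power 0.802 at 64 per group and 0.794 at 63. It matters here only because 2 × 64 = 128 is used as an illustrative sample size below.

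**Step 1: is there a route from past failures to expectation?** The synopsis says potentially, without direction. Appendix 7 adds a concrete route in the intervention group, because the number of previous failed cycles enters the prognosis those couples are shown, with coefficient -0.088 (standard error 0.070, P = 0.205). The coefficient is imprecise, but the formula uses its point value. With all other inputs equal, four more failed cycles multiply the odds by exp(4 × -0.088) = exp(-0.352) = 0.703. Starting from the specimen prognosis in Appendix 5, 38.39%, the odds are 0.3839/0.6161 = 0.623. Then 0.623 × 0.703 = 0.438, and 0.438/1.438 = 30.5%. This concerns the prognosis shown. How far patients' own expectation follows it is not known.

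**Step 2: effect of leaving the term out.** In standardised units, let bE and bF be the effects of expectation and of past failures on distress, and r the correlation between expectation and past failures. Then

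slope without the failure term = bE + bF × r.

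The documents give none of these values. Assuming bE = 0.20:

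| r | bF = 0.1 | bF = 0.2 | bF = 0.3 |
|---|---|---|---|
| -0.5 | 0.15 | 0.10 | 0.05 |
| -0.3 | 0.17 | 0.14 | 0.11 |
| -0.1 | 0.19 | 0.18 | 0.17 |
| 0 | 0.20 | 0.20 | 0.20 |
| 0.1 | 0.21 | 0.22 | 0.23 |
| 0.3 | 0.23 | 0.26 | 0.29 |
| 0.5 | 0.25 | 0.30 | 0.35 |

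The shift is bF × r whatever bE is. It runs from 0.3 × -0.5 = -0.15 to 0.3 × 0.5 = +0.15 SD, and is zero if r = 0 or bF = 0. The table treats persons as independent, which corresponds to the separate models per gender.

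**Step 3: what one slope does with a combined effect.** Assumed truth, standardised: distress = 0.20 × expectation × failures + 0.20 × failures + noise (SD 0.95). The slope of distress on expectation is then -0.20 one SD below the mean failure count, 0 at the mean and +0.20 one SD above. Simulation with 128 independent persons and 4,000 runs gave:

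- r = 0: expectation-only slope about 0.00.
- r = -0.3: expectation-only slope -0.059, which agrees with bF × r = 0.20 × -0.3 = -0.06.
- With the failure count and the product term added, each is recovered at about 0.20. Power for the product term is 61% (r = 0) and 64% (r = -0.3).

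In this scenario the planned slope contains no trace of the combination, whatever the value of r.

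**The case against.** The strongest reply is that the model does what the plan sets out to do. A reader might infer that section 4.6 fails to test the plan's own hypothesis. The documents do not support that. The only formal hypothesis, in section 2.1, concerns the effect of feedback on overestimation. The combination is background from interviews, section 1 names the simple association as the gap, and section 2.2 sets a simple exploratory aim that the model matches. The statement in section 3.1.1 concerns discontinuation, not distress, so it bears on section 4.7. All of this stands.

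A reader might also infer that the slope is known to be biased, and by a definite percentage. That is not supported either. The synopsis gives no direction for the effect on expectation, and section 1 describes failure together with high expectation, not an independent effect of failure on distress. Any percentage would further depend on an assumed spread of expected rates that the documents do not give.

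The random couple factor offers partial protection. The failure count is essentially a couple-level value, so differences between partners within a couple are not confounded by it. But a random factor still uses differences between couples, and the per-gender models use nothing else.

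Finally, restricting entry to 2nd-6th cycles narrows the range of failure histories, but it still leaves variation.

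**Conclusion.** The point holds in a limited form. The section 4.6 slope is an unadjusted, observational association that leaves out a baseline value already collected and thought by the plan to bear on expectation. Whether this matters depends on two relations the documents do not quantify. Over the assumed ranges the shift lies between -0.15 and +0.15 SD, with zero possible. Independently of that, a model without a product term cannot show the combination described in section 1. This is a limit on what the result can say, not a mismatch with the stated aim.

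Severity is low. The analysis is exploratory, and the primary outcome, the sample size and the randomised between-group IDS comparison in the same section are unaffected.

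**What to change.** In section 4.6, add the number of past unsuccessful embryo transfers as a covariate and report the adjusted slope beside the unadjusted one. The value predates randomisation, so adjusting for it does not condition on a consequence of the intervention.

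As an addition labelled exploratory, include the product of that count with the expected rate. Report the slope with its 95% confidence interval at a low and a high failure count (for example the sample quartiles), whatever the interaction p-value.

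Section 4.7 names no model for expectation and discontinuation. When one is written, apply the same adjustment there, since section 3.1.1 gives the corresponding rationale.

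If the sponsor prefers to keep the model as it is, one sentence should say that the slope is unadjusted and does not address the combination in section 1.

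The cost is a few lines of analysis-plan text and one extra model run on data already being extracted. The drawback is an imprecise interaction estimate: power is only about 61-64% with 128 independent persons, even for an assumed standardised interaction of 0.20. The interval should therefore carry the message, not the p-value.
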